- (1) HPE Skincare: Intensive Hydrating Elixir (active ingredient: HPE)
- (2) Market-competitor: Skinceuticals C.E. Ferulic (active ingredients: Vitamin C, Vitamin E and ferulic acid serum).

IND application was not submitted to the FDA (cosmetic use, herbals, botanicals, supplement). These products are currently available over-the-counter for cosmetic use (www.hpeskincare.com).

HPE is an extracellular vesicle (EV) product manufactured by industry sponsor, RION (Rochester, MN). It represents a novel off-the-shelf regenerative cosmetic product for skin rejuvenation. HPE is a leukocyte depleted allogeneic product derived from human U.S. sourced pooled apheresed platelets (derived from screened healthy donors). HPE is comprised of platelet conditioned medium derived extracellular vesicles rich in anti-inflammatory and angiogenic growth factors. HPE is aseptically processed, pyrogen-free and does not contain preservatives. Sourced platelets are received by a compliant manufacturing facility from FDA registered/licensed blood banks, where they remain frozen until further processing. At that time platelets are thawed, lysed, filtered through a leukocyte reduction filter and undergoes staged sterile filtration to further eliminate cell, cell fragments and non-EV subcomponents prior. Following pooling and serial freeze-thaw cycles derived HPE EVs are lyophilized and packaged. The end-product consists of platelet extracellular vesicles rich in anti-inflammatory cues and antioxidant enzymes, is manufactured without addition of any excipients, compounds, preservatives, or biologically active molecules. This product has undergone human repeat insult patch testing on 100 subjects without any evidence of skin sensitization and has been tested in a collagen formulation, documenting anti-aging impact around the eyes in a 35-subject study.

HPE was developed with partnership from Vanicream (Pharmaceutical Specialties, Inc., Rochester, MN) and formulated without parabens, petrolatum, phthalates, and SLS. Plus, it's fragrance-free.

INTENSIVE HYDRATING ELIXIR

BATCHNO.001

HYDRATE+RESTORE

HPE SKINCARE

Usage: Before applying to face or targeted areas, use a gentle exfoliating cleanser. We recommend applying in the morning and night. Wait 10-15 minutes or until fully absorbed before layering with additional products.

[figure not shown]

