Lauded for its superior antioxidant benefits, this highly potent form of pure vitamin C helps neutralize free radicals and protect against oxidative stress while providing visible anti-aging henefits

1% alpha tocopherol

This pure form of vitamin E neutralizes free radicals and replenishes skin lipids. It has been proven to act synergistically with vitamin C.

0.5% ferulic acid

A plant-based antioxidant, ferulic acid neutralizes free radicals and enhances the antioxidant benefits and stability of vitamins C and E.

Learn more about L-ascorbic acid

Learn More About Ferulic Acid

See All Ingredients

aqua / water / eau, ethoxydiglycol, ascorbic acid, glycerin, propylene glycol, laureth-23, phenoxyethanol, tocopherol, triethanolamine, ferulic acid, panthenol, sodium hyaluronate

Study Design and Methods

Methods: Describe in lay terms, completely detailing the research activities that will be conducted by Mayo Clinic staff under this protocol.

80 participants over the age of 40 with moderate photoaging (dyschromic facial skin with fine lines and wrinkles) will be recruited from Mayo Clinic Center for Aesthetic Medicine and Surgery (CAMS) to participate in this study. After signing written informed consent, eligible subjects will be instructed to apply topical HPE to entire face and decolletage twice daily, in the morning and at bedtime. In addition, subjects will be instructed to apply topical HPE to the right dorsal hand and market-competitor group (SkinceuticalsTM C.E. Ferulic) to left dorsal hand. Select subjects (n=20) will also apply topical HPE to the right upper inner arm for skin biopsies at week 12. A baseline skin biopsy will be obtained from untreated skin on the left upper inner arm from the same subjects. Subject renumeration will be provided for skin biopsies.

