- 3. Individuals with a history of any dermatological disease or condition, including but not limited to active atopic dermatitis, psoriasis, eczema, active seasonal allergies, collagen diseases, or skin cancer involving the treated sites within the past 6 months
- 4. Cutaneous marks on the experimental area which could interfere with the assessment of skin reactions (pigmentation problems, scar elements, over-developed pilosity, ephelides, and nevi in too great quantity, sunburn, beauty spots, freckles, etc.)
- 5. Participants with asymmetric photodamage on dorsal hands due to environmental exposures (i.e., golfing) and/or other skin lesions including burns or scars resulting in significant skin surface variability between dorsal hands
- 6. Eczematous reaction still visible, scar, or pigmentary sequelae of previous tests on the experimental area
- 7. Allergy to colophony or nickel.
- 8. Allergy or reactivity to drugs, food or cosmetic products previously observed, including perfumes or cologne products.
- 9. Skin hyper-reactivity.
- 10. Forecast of intensive sun, tanning bed use or UV phototherapy during the test period.
- 11. Treatment with prescription-strength Vitamin A acid or its derivatives within 3 months before the beginning of the study.
- 12. Treatment with topical steroids on the experimental area within 16 days before the study.

Study constraints:

- 1. No application of products on the experimental area (except the suggested ones), particularly any antiaging cosmetic products except for sunscreen.
- 2. No change in hygiene habits
- 3. No application of any cosmetic moisturizing products on the face or any makeup on face and lips, on the day of study evaluations
- 4. No change in the way of life or in the physical activity

5. No change in dietary activities, or any treatment that significantly impacts body weight

Effective: 9/20/2017

- 6. No exfoliating treatment on the experimental areas
- 7. Description of any treatment undertaken during the study and all eventual deviations

Review of medical records, images, specimens					
Check all that apply (data includes medical records, images, specimens).					
Only data that exists before the IRB submission date will be collected.					
Date Range for Specimens and/or Review of Medical Records: Examples: 01/01/1999 through 12/31/2015, or all records through mm/dd/yyyy.					
Note: The Date Range must include the period for collection of baseline data, as well as follow-up data, if applicable.					

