 The study involves data that exist at the time of IRB submission and data that will be generated after IRB submission. Include this activity in the Methods section. Examples The study plans to conduct a retrospective chart review and ask subjects to complete a questionnaire. The study plans to include subjects previously diagnosed with a specific disease and add newly diagnosed subjects in the future. 					
The study will use data that have been collected under another IRB protocol. Include in the Methods section and enter the IRB number from which the research material will be obtained. When appropriate, note when subjects have provided consent for future use of their data and/or specimens as described in this protocol.					
Enter one IRB number per line, add more lines as needed					
Data Specimens Data & Specimens					
☐ Data ☐ Specimens ☐ Data & Specimens					
☐ Data ☐ Specimens ☐ Data & Specimens					
Data Analysis					

Power analyses may not be appropriate if this is a feasibility or pilot study, but end-point analysis plans are always appropriate even if only exploratory. Provide all information requested below, or provide justification if not including all of the information.

Data Analysis Plan:

All continuous data will be analyzed using independent 2-group t tests and reported as means \pm standard deviations. Categorical data will be compared between the 2 groups using chi-square tests and reported as counts and percentages. Nonparametric equivalents Wilcoxon rank-sum and Fisher exact tests will be used as needed for nonnormal distributions and low variable numbers, respectively. Treatment effects on outcomes will be compared between baseline versus HPE and HPE versus market competitor group with a significance level of p < 0.05.

Endpoints

Primary:

Evaluation of the tolerability of the study product.

- a. Nature, incidence, and severity of adverse events (AEs)
 - 1) Defined as any untoward or undesirable medical occurrence in the form of signs, symptoms, abnormal findings, or diseases that emerge or worsen relative to baseline (i.e., if present upon study entry) during the study regardless of causal relationship.
 - 2) Assessment
 - i. Incidence and severity of AEs (mild, moderate, severe)
 - ii. Relationship of AEs to study product (probable, possible, unlikely, unrelated)
 - 1. If possibly or probably related to the study product, determine whether related to the product itself or procedures pertaining to delivery of the study product.

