 - iii. Incidence of serious adverse events (SAEs) defined as AEs that result in death, life threatening adverse experiences, hospitalization, new or prolonged disability/incapacity, persistent or significant congenital defect/anomaly, or other events that in the opinion of the PI may have adversely affected the rights, safety, or welfare of the subjects or others, or substantially compromised the research data.
 - 3) Methods
 - i. Spontaneous subject reports
 - ii. Subject interview by study personnel
 - iii. Clinical examination during face-to-face clinic follow-ups
 - 4) Timing
 - i. Baseline
 - ii. 6-week post-treatment (acute)
 - iii. 12, 26- and 52-weeks post-treatment (delayed)

Change in photoaging scores from Baseline at 6,12, 26- and 52-weeks.

a. Canfield VISIA CR Gen 5 with 3DPrimos will be used to evaluate qualitatively and quantitatively skin profile changes (color evenness and roughness measurements), and to assess wrinkle count, depth, and volume by a full-aligned facial and bilateral dorsal hands images.

Information about Canfield VISIA CR is a high-resolution clinical imaging system (21 Megapixel resolution 45MP Canon EOS R5) which uses LED lighting. No radiation-based exposure. It captures high-resolution

photographic images. More information on prior model (without 3D Primos): https://www.canfieldsci.com/common/docs/products/1/brochures/VISIACRBrochure.pdf

Secondary:

- 1) Dermatopathologic evaluation of the skin
 - a) Skin microbiome: To define skin facial microbial clades, a standard swab and tape stripping method will be used on all interested subjects. Both methods are minimally invasive and can yield optimal results. All subjects will be offered skin microbiome analysis unless they did not meet criteria (i.e., washed face 3-hours prior to clinical visit, which would shift the skin microbiome; or prior allergy to adhesives) or unless they decline
 - i) Skin microbiome: Skin swab collection (n=80)
 Skin bacteria will be collected by the swabbing method as described in previous studies [4]. In brief, the left and right malar cheeks will be gently swabbed with a single dry cotton swab in a Z-stroke manner [5]. For skin microbiome, the swab head will be stored in a sterile 1.5-mL centrifugation tube at -80°C until ready for analysis.
 - ii) Skin microbiome: Tape-stripping collection (n=80)

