Informed consent must be obtained with signing of the ICF prior to performing any study-related procedure.

Assessments during the screening visit will include:

- Demographic data
- Medical and surgical history
- Medication history
- Concomitant medication
- Concomitant procedures
- Physical examination

Based on the result of the screening visit and review of the eligibility criteria, the PI will assess each potential subject's eligibility for study inclusion. If the subject is found eligible, she can then be enrolled. The screening visit results will be recorded in the subject's electronic case report form (e-CRF) and the subject will be scheduled for a subsequent visit to complete additional baseline assessments,

Enrolled subjects will then initiate baseline visit (V0) at the same time during which they will complete their baseline assessments and initiate their treatment.

General assessment

- Baseline VISIA-CR imaging
- Photography
- Skin microbiome facial swab and tape-stripping (n=80 skin swab and tape-stripping)
- Skin biopsy (n=30)
 - o Left upper inner arm (untreated skin)

Treatment

- Treatment: Topical HPE twice daily for study duration.
- Study staff will demonstrate treatment application.
- Subject instructions and treatment log will be provided.
- Each subject will receive the first cosmetic kit, which will include gentle cleanser, unscented bar soap, HPETM product, SkinceuticalsTM CE Ferulic serum, sunscreen and moisturizer. A second cosmetic kit will be provided at week 6 visit.

• For questions, subjects will be provided contact email: [contact]

Visit 1: Follow-up at 6-weeks

- VISIA-CR imaging
- Photography
- Topical treatment jars will be weighed to ensure correct application amount.
- Subject treatment log will be reviewed.

Specific assessment (cosmetic evaluation questionnaires)

- Global Aesthetic Improvement Scale
- Cosmetic Improvement Scale

Treatment assessment

- Continuation of Topical HPE twice daily as indicated.
- Study staff will re-demonstrate treatment application.
- Each subject will receive their second cosmetic kit, which will include gentle cleanser, unscented bar soap, HPETM product, SkinceuticalsTM CE Ferulic serum, sunscreen and moisturizer.
- For questions, subjects will be provided contact email: [contact]

Visit 2: Follow-up at 12-weeks

- VISIA-CR imaging
- Photography
- Skin microbiome facial swab and tape-stripping (n=80 skin swab and tape-stripping)
- Skin biopsy (n=30)
 - Right upper inner arm (HPE)

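### The visit-day moisturizer rule names only the face, so HPE and other kit products may be on the imaged dorsal hands at weeks 6 and 12, while baseline hand images carry no study product

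*Combined protocol and SAP*

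**What the plan says.** Three provisions bear on what may be on the skin when images are taken.

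- **Visit-day rule.** Study constraints, item 3: "No application of any cosmetic moisturizing products on the face or any makeup on face and lips, on the day of study evaluations". The hands are not mentioned.
- **General rule.** Study constraints, item 1: "No application of products on the experimental area (except the suggested ones", with sunscreen also let through. This rule is not tied to a site or to visit days.
- **Dosing.** The Treatment list under the baseline visit gives "Topical HPE twice daily for study duration", and the Methods specify morning and bedtime. Subjects are to "apply topical HPE to the right dorsal hand and market-competitor group" product to the left. The kit given at baseline and again at week 6 also holds a moisturizer and a sunscreen.

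The photoaging endpoint under Primary takes color evenness, roughness and wrinkle count, depth and volume from "full-aligned facial and bilateral dorsal hands images". Table 1 schedules this imaging at every visit, and Figure 1 lists weeks 0, 6 and 12 for the left hand. The Data Analysis Plan states that "Treatment effects on outcomes will be compared between baseline versus HPE and HPE versus market competitor group".

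The only other visit-day preparation rules concern microbiome sampling of the cheeks. The text gives no washing, waiting or dose-holding instruction for the hands before imaging.

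**The concern.** The plan treats same-day moisturizer as worth controlling on one imaged site and does not name the other. On that other site, the dosing instruction itself puts product on the skin on the morning of a follow-up visit. The product is listed as "HPE Skincare: Intensive Hydrating Elixir (active ingredient: HPE", and its ingredients include glycerin and hyaluronic acid.

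At baseline the position differs, because the first dose follows the baseline assessments. A before-and-after comparison on the right hand can thus set skin without study product against skin that may have been treated an hour or two earlier. If a humectant film changes roughness or wrinkle readings, part of the measured change would belong to the day of the visit and not to 6 or 12 weeks of use. The data would not allow the two to be separated.

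**Working it through.** No figure in the plan needs reproducing, and the documents give no variance or effect size for the hand measures. The check compares what the text allows on the hands at each visit, then counts assessments.

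**What may be on the dorsal hands at imaging**

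| Product | Baseline | Weeks 6 and 12 | Source |
|---|---|---|---|
| HPE (right) | No; treatment starts at this visit | Yes; morning dose is scheduled | Baseline visit; Methods |
| Competitor (left) | No | Yes; described as a daytime serum, frequency not given | Product description |
| Kit moisturizer | No; kit not yet issued | Yes; a suggested product | Item 1; kit list |
| Sunscreen | Yes; exempt | Yes; exempt | Item 1 |
| Subject's own cream | Reasonably barred | Reasonably barred | Item 1 |

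The last row takes the experimental area, which the protocol does not define, to include the hands because they are treated and imaged.

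**What this does to each comparison.** Let *D* be the lasting effect of a product at a follow-up visit, and *s* the same-day surface effect of whatever is on that hand at imaging.

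- Right hand, baseline versus HPE: observed change = *D*(HPE) + [*s*(right, follow-up) − *s*(right, baseline)].
- Right versus left, in change from baseline: observed difference = [*D*(HPE) − *D*(competitor)] + [*s*(right) − *s*(left)] at follow-up − [*s*(right) − *s*(left)] at baseline.

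In the first line, nothing in the plan makes the bracket zero. If product smooths the skin, product at follow-up only would favor HPE, something on the hand at baseline only would work against it, and product at both would partly cancel.

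In the second line, the follow-up terms partly cancel because both ingredient lists contain glycerin, panthenol and hyaluronic acid or its sodium salt. They need not cancel fully, because the formulations differ and the competitor's dosing frequency is not stated.

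**Counts at full accrual and attendance (main study, 80 subjects)**

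- Right hand, weeks 6 and 12: 80 x 1 x 2 = 160 assessments.
- Left hand, weeks 6 and 12: 80 x 1 x 2 = 160 assessments.
- Both hands at follow-up: 160 + 160 = 320.
- Both hands at baseline: 80 x 2 = 160.

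The follow-up figures count assessments without a rule on same-day study product. They do not measure an effect.

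**Left out.** After week 12, HPE continues on face and decolletage only, so weeks 26 and 52 are not counted. The 50 subjects of the 2X substudy have face and neck imaging only.

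**The case against.** Much of the case on the other side stands.

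- **Item 1 already protects the hands.** A reader might infer that product on the hands is wholly uncontrolled, baseline included. The documents do not support that. Item 1 sits in the same list as item 3, with no separate start date, and reasonably bars a subject's own hand cream at baseline. The visit text is ambiguous: one sentence speaks of scheduling a later visit for baseline assessments, and the next has enrolled subjects begin the baseline visit "at the same time during which they will complete their baseline assessments and initiate their treatment". That is a reason to tell subjects early, not evidence that the rule fails to bind. What item 1 does not reach is the exempted products.
- **Unseen material may cover it.** Subject instructions and a treatment log are provided, and neither is reproduced. A hand-preparation instruction may exist there. Even so, the written constraint singles out the face, and the protocol is where the rule belongs.
- **The effect may be gone by imaging.** The HPE usage text advises waiting 10 to 15 minutes, or until absorbed, before layering other products. That concerns layering; it shows neither that a surface effect has ended nor that it lasts for hours. Duration remains an assumption either way.
- **Usual-use imaging is defensible, and holding a dose can do harm.** For a cosmetic study, imaging skin as normally treated is a reasonable choice, and with both products on that morning the hands are comparable. If the competitor is used once each morning and only the visit-day dose is held, about 24 h would have passed since its last dose, against about 8 to 12 h since the bedtime HPE dose (assumed clock times). This stands, and the fix has to deal with it.

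**Conclusion.** The point holds as a minor design gap. The plan's visit-day rule omits an imaged site, and its own dosing instruction can place study product there at weeks 6 and 12 but not at baseline. The comparison most exposed is right-hand baseline versus HPE. The right-versus-left contrast is partly protected.

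The conclusion rests on two assumptions: that same-day product can alter roughness or wrinkle measures at the time of imaging, and that the experimental area in item 1 includes the dorsal hands. The size in outcome units cannot be derived.

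A reader might go further and infer that the hand results are biased toward HPE. The documents do not support this, because the net direction depends on what is on the skin at each visit and no data on that are given. Nor do they support extending the point to the face, where the natural reading of item 3 already takes in a hydrating product, or to the tolerability endpoint.

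**What to change.** Extend item 3 to both dorsal hands. On imaging days at baseline, week 6 and week 12, no moisturizer, sunscreen or study product goes on either hand until the images are taken. Tell subjects this before the baseline visit.

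Hold both study products on the same schedule, and require the last dose of each before the visit to be taken at the same time on both hands, so that time since last dose is equal. If the competitor is a once-daily morning product, the amendment must say which dose is the last for both hands; holding only the visit-morning dose would not be enough. Note the time of last application for each hand in the existing treatment log.

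The cost is one amended sentence, one log entry and one delayed morning dose per follow-up imaging visit, which is two per subject (weeks 6 and 12). Two limits remain: residue from the preceding dose, and the lack of a vehicle control.

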Additionally, Canfield shall take all appropriate technical and organizational measures which are necessary to prevent the unauthorized or unlawful processing of, the unauthorized or unlawful disclosure of and/or the accidental loss or destruction of, or damage to, such data, including without limitation, implementation and enforcement of administrative, technical and physical security policies and procedures. Incident Reporting. Canfield shall promptly notify Sponsor in the event of a security breach or incident involving any data which Canfield is processing on behalf of Sponsor.

Study procedures

The skin biopsies, skin swabs and long-term follow-up visits will be obtained separately from 80 subjects.

- n=80 subjects
- Entire face and decolletage HPE (n=80)
- HPE (n=80) to be applied on the right dorsal hand
- Skinceuticals CE Ferulic (n=80) to be applied on the left dorsal hand
- Skin biopsy (baseline): Left upper inner arm untreated (n=30)
- Skin biopsy (week 12): Right upper inner arm HPE treated (n=30, same subjects as above)
- Microbiome analysis (baseline): Left and right malar cheek untreated (n=80 with both skin swab and tape-stripping method)
- Microbiome analysis (week 12): Left and right malar cheek HPE treated (n=80 with both skin swab and tape-stripping method)

N=30 - Skin biopsy: Two total skin biopsies will be performed per subject (n=30 subjects). In this study, we will remove a small piece of skin from untreated skin on the left upper inner arm (baseline) and HPE treated area on the right upper inner arm (week 12). This is called a skin biopsy.

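### The plan names only unpaired tests, but both planned contrasts are within-person; if the within-person correlation is positive, p-values are too large and real differences may be missed

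*Combined protocol and SAP*

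**What the plan says.** The Data Analysis Plan sets the test for every continuous outcome: "All continuous data will be analyzed using independent 2-group t tests". Categorical data get chi-square tests between two groups. The fallbacks are also tests for independent samples: "Nonparametric equivalents Wilcoxon rank-sum and Fisher exact tests will be used as needed". The same paragraph names the contrasts: "Treatment effects on outcomes will be compared between baseline versus HPE and HPE versus market competitor group", at p < 0.05.

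The design elsewhere in the protocol is as follows.

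- **Hands.** Study procedures puts HPE on the right dorsal hand of 80 subjects and the competitor on the other hand of the same 80: "Skinceuticals CE Ferulic (n=80) to be applied on the left dorsal hand". There is no separate competitor group.
- **Imaging.** The second primary endpoint is "Change in photoaging scores from Baseline at 6,12, 26- and 52-weeks", measured repeatedly in the same subjects.
- **Biopsies.** The baseline sample comes from the left arm and the week-12 sample from the same people: "Right upper inner arm HPE treated (n=30, same subjects as above".
- **Microbiome.** The same cheeks are sampled at baseline and week 12.

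No paired t test, signed-rank test, McNemar test or model with a subject effect appears in the document.

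**The concern.** An independent-samples test treats the two sets of values as coming from unrelated people. Here each person supplies both values, so person-to-person variation cancels in the difference. The unpaired test puts that variation back into the standard error.

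Positive correlation is plausible because the same person is measured twice. For the hands there is further support in Exclusion Criterion 5, which removes "Participants with asymmetric photodamage on dorsal hands due to environmental exposures".

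With positive correlation the error is conservative. It does not create false positives, but it can hide a real change from baseline, or a real difference between the products in either direction. The third stated aim is a comparison with a marketed competitor, so an inflated p-value there could also be misread as evidence that the products are similar.

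The concern covers outcomes with a paired value: imaging, histology and scalar microbiome summaries. It does not cover adverse event incidence, or the two improvement scales where each person rates once with no baseline value.

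**Working it through.** The plan states no power, effect size, SD or correlation, so there is no figure of its own to reproduce. The check asks what the named test does to paired data.

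**Inputs from the document.** n = 80 hand or face pairs. n = 30 biopsy pairs (Endpoints, Study procedures) or n = 20 (Methods: "Select subjects (n=20) will also apply topical HPE to the right upper inner arm for skin biopsies at week 12"). Significance level 0.05.

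**Assumptions.** Two-sided test, normal data, equal SDs, complete pairs, and within-person correlation ρ varied from 0 to 0.7.

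**Standard errors.** The unpaired test uses SD·√(2/n). The true standard error of the mean difference is SD·√(2(1−ρ)/n). The ratio is 1/√(1−ρ): 1.20, 1.41, 1.58 and 1.83 at ρ = 0.3, 0.5, 0.6 and 0.7. For example, at n = 80 and ρ = 0.5 the unpaired standard error is 0.158 SD and the true one is 0.112 SD.

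**Rejection rates (normal approximation).**

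- Actual type I error of the unpaired test: 2Φ(−1.96/√(1−ρ)).
- Its power at the difference where the paired test has 80% power: Φ(2.80 − 1.96/√(1−ρ)), with 2.80 = 1.96 + 0.84.

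At ρ = 0.5, 1.96/√0.5 = 2.77. Type I error is therefore 2Φ(−2.77) = 0.56%, and power is Φ(0.03) = 51%.

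Results for n = 80, with power also simulated from bivariate normal pairs (40,000 trials per cell):

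| ρ (assumed) | Type I error, formula | Power, formula | Power, simulated |
|---|---|---|---|
| 0 | 5.0% | 80% | about 80% |
| 0.1 | 3.9% | 77% | 77–78% |
| 0.3 | 1.9% | 68% | 68% |
| 0.5 | 0.56% | 51% | 52% |
| 0.6 | 0.19% | 38% | 39% |
| 0.7 | 0.04% | 22% | 23% |

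The paired test held about 5% type I error at every ρ simulated. More than half of the 80% power is lost only from ρ of about 0.6.

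**Fixed effects, n = 80, ρ = 0.5 (unpaired against paired, simulated).** 0.2 SD: 16% against 42%. 0.3 SD: 46% against about 76%. 0.5 SD: 95% against 99%.

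**Rank tests.** In a smaller simulation (6,000 trials per cell) at ρ = 0.5, rank-sum had 48% power and signed-rank 78%.

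**Biopsies.** From 80% paired power, the unpaired test falls to about 53% (n = 30) or 54–55% (n = 20) at ρ = 0.5, and to about 25% or 27% at ρ = 0.7.

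**Which ρ applies where.** For raw baseline against follow-up, ρ is the correlation between the two visits; for biopsies it is between the two samples. If the hands are compared on change from baseline, ρ is the correlation between the two hands' changes. Subtracting baseline removes the stable personal level that the hands share, so this ρ can be well below that for raw values. Taking it as 0.10 to 0.42 (an assumption), the formula gives Φ(2.80 − 2.07) = 77% down to Φ(2.80 − 2.57) = 59%. Simulation gives about 78% to 59%.

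**The case against.** The strongest counter-argument is about size. No correlation is stated, so the loss may be nil. No power target is set, so no promised power is breached. For a large effect (0.5 SD at ρ = 0.5) the choice of test hardly matters. The imaging endpoint is a change score, so the lower range applies to the hand comparison, and the 23% figure should not be attached to it. The exclusion of asymmetric hands supports correlation of raw hand values only, not of changes, faces or arms. Inclusion Criterion 4 also restricts facial wrinkling to mild-to-moderate, which narrows between-person spread and could lower ρ for the face. Tolerability, the first-listed primary endpoint, is unaffected.

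All of this stands as a limit on magnitude, and the figures above are labelled by contrast for that reason. The conservative direction also depends on ρ not being negative: at ρ = −0.3, unlikely here, type I error would be about 8.6%.

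None of it rescues the choice of test. The mismatch does not depend on ρ; only its cost does. The unpaired tests might suit a comparison of the 50-person 2X substudy with the main cohort, but the plan names no such contrast, and the substudy's own repeated visits are again within-person.

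**Conclusion.** The concern holds. Every test named assumes independent groups, and both named contrasts are within-person, including the one behind the imaging primary endpoint. This is wrong as written, not merely under-specified, and should be corrected before analysis. Confidence in the mismatch is high.

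The size of its effect is uncertain. It runs from no loss (ρ near 0, or a large effect) to severe loss (high ρ with a small effect). All the power figures rest on assumed correlations, normality, equal SDs and complete pairs. Week 26 and 52 visits and microbiome sampling are optional, so actual pair numbers may be lower.

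**What to change.** Amend the Data Analysis Plan as follows.

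1. For within-person contrasts, use a paired t test, or a Wilcoxon signed-rank test where normality fails, on within-person differences. Report the mean difference with a 95% confidence interval and the number of complete pairs.
2. For the hands, analyse the right-minus-left difference in change from baseline at each visit, or the right-minus-left follow-up difference adjusted for the baseline difference. State which one.
3. Use exact McNemar only for a binary outcome measured on both members of a pair. If questionnaires are completed per hand, as the Figure 1 text may imply, treat those ratings as pairs.
4. Summarise adverse events and once-per-person ratings descriptively. For the microbiome, apply paired tests only to scalar summaries.
5. Keep unpaired tests for contrasts between different people. Apply the paired methods to the 2X substudy's repeated measures as well.
6. Reconcile the biopsy number: 20 in Methods, 30 in Endpoints and Study procedures.

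State the limits that pairing does not remove. Product is confounded with hand side. The biopsy contrast is confounded with side and time. A non-significant hand result does not show similarity. Paired tests also restore each comparison to its full 5% error, so the many measures, sites and visits still need a stated approach to multiplicity.

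The cost is a few sentences, with no new data, visits or subjects.
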